	APPENDICES	30
	APPENDIX A: SCHEDULE OF EVENTS	31

LIST OF ABBREVIATIONS

The following abbreviations describe terms, documents and study personnel used in the conduct of this study protocol.

AE	Adverse Event/Adverse Experience
CC	Coordinating Centre
CIOMS	Council for international Organizations of Medical Sciences
CRF	Case Report Form
CCTS	Centre for Clinical Trial Support
EC	Ethics Committee
ICH	International Conference on Harmonisation
IP	Investigational Product
pCRF	Paper Case Report Form
GCP	Good Clinical Practice
ICF	Informed Consent Form
PHI	Personal Health Information
PI	Principal Investigator
PM	Product Monograph
QI	Qualified Investigator
REB	Research Ethics Board
RCT	Randomized Controlled Trial
SAE	Serious Adverse Event/Serious Adverse Experience
SOP	Standard Operating Procedure
SRI	Sunnybrook Research Institute
SUADR	Serious and Unexpected Adverse Drug Reaction
TMF	Trial Master File

PROTOCOL SUMMARY

Protocol Title (Short Title)	DIAgnosing GDM usiNg Oral Sugar InStead (DIAGNOSIS)
	Randomized crossover study comparing the standard glucose beverage and Dex4® tablets for 2 hour oral glucose tolerance testing in pregnant women with a positive screen on the 50g glucose tolerance challenge for gestational diabetes
Protocol Number	Assigned REB number 418-2018.
Phase	II
Study Design	Phase II randomized controlled crossover study
Study Duration	6 months
Setting	Single-centre
Sample Size	28 required by power calculation, aiming to recruit 42 (accounting for 33% loss)
Main Inclusion Criteria	
 • Positive 50g GCT result between 7.8-11.0 mmol/L • singleton pregnancy
Primary Outcome(s):	2 hour serum glucose value after the carbohydrate challenge. The study is powered to assess equivalence between Dex4® tablets and 75g of glucose beverage.
Secondary Outcome(s):	Side effects associated with Dex4® tablets and participant preference of using Dex4® tablets or the standard glucose beverage for OGTT testing.
Investigational Product (IP) and Planned Use	The investigational product to be used is (Dex4®) dextrose monohydrate tablets, containing 4g of dextrose monohydrate per tablet equivalent to 3.64g of dextrose anhydrous. After a minimum 8 hour fast, 21 Dex4® tablets will be ingested over the span of 5 minutes. Venous blood sampling for serum glucose will be taken prior to ingestion , and 1 and 2 hours (+/- 15 minutes) after ingesting the Dex4® tablets.
Statistical Analysis:	To evaluate equivalence, the mean of the differences at each time point (fasting, 1 hr and 2 hrs after glucose beverage/Dex4® tablets) will be calculated and a two-sample equivalence-test will be used to compare the means. Based on previous reports of intra-individual variation in 2 hour OGTT of 16.7% for serum glucose measurement (21), Dex4® tablets will be considered equivalent to glucose beverage if the equivalence margin is less than or equal to 20%.

2 INTRODUCTION

This study document is the protocol for research involving human participants. This study is to be conducted according to Canadian and international standards, and in compliance with the protocol, International Conference on Harmonisation Good Clinical Practice E6 (ICH-GCP), World Medical Association Declaration of Helsinki: Ethical Principles for Medical Research Involving Human Participants, as well as applicable regulatory and institutional requirements and research policies.

2.1 Background

Gestational diabetes mellitus (GDM) is defined as any degree of hyperglycemia with onset or first recognition during pregnancy (5-6). Up to 70% of women with GDM will develop type 2 diabetes mellitus (T2DM) during their lifetime (3). Diabetes Canada and the Society of Obstetricians and Gynecologists of Canada recommend that pregnant women be screened for GDM between 24-28 weeks of pregnancy (7,8). The current 2-step approach for GDM detection involves a screening test and a diagnostic test, both of which use a liquid glucose challenge. In Canada, most pregnant women routinely undergo screening for GDM by consuming 50g of a liquid glucose solution and having a blood test for serum glucose after 1 hr, this test is commonly known as the 50g glucose challenge test (50g GCT). Women with a positive screening test (serum glucose 7.9 to 11.0 mmol/L) take a second test to confirm the diagnosis. For the second test, called a 2 hour oral glucose tolerance test (OGTT), women fast for 8 hours and then consume 75g of glucose beverage, and serum glucose levels are taken at fasting, 1 and 2 hours after drinking the glucose beverage. The 75g OGTT is the gold standard and is performed for GDM diagnosis.

Unfortunately, up to 30% of women do not tolerate glucose beverage (9-11). Side effects include: nausea, vomiting, bloating, abdominal pain, diarrhea, sweating and headache which may prevent them from completing testing for GDM (9-11). If women cannot complete screening, the diagnosis of GDM may be missed, increasing the risk of complications for mothers and their babies, such as a larger baby and trauma during delivery. Women who have had a history of GDM are at higher risk of developing cardiometabolic complications such as lipid abnormalities, hypertension and hyperinsulinemia (5, 15). GDM also carries a risk for later development of T2DM to the mother and fetus (2, 3). Unfortunately, GDM prevalence has doubled in the past 10 years in all ethnic populations and reaches 25-32% in some (16-19), with an estimated 19% of cases proceeding on to become T2DM within the first 9 years after pregnancy (2). Because of T2DM's long asymptomatic phase, many women will have already developed health complications by the time they are diagnosed. A missed diagnosis of GDM is a missed opportunity to intervene and offer prevention for T2DM.

Other alternatives to the standard glucose beverage such as jelly beans and candy twists (Twizzlers) have been suggested in the literature but are limited by their diagnostic accuracy and portion size, respectively (13). However, Dex4® tablets may not have this issue. As Dex4® tablets are normally used to correct hypoglycemia in people living with diabetes, portion sizes

are manufactured to be more precise compared to most candies, and lots are regularly analyzed to confirm tablet size, hardness, and dextrose monohydrate content.

The purpose of this study is to compare the positive and negative effects of Dex4® tablets, as an alternative form of fast acting carbohydrate, compared to the current standard diagnostic test, glucose beverage. We hypothesize that because of their availability in solid, chewable form, variety of flavours and lack of carbonation, Dex4® tablets may result in fewer side effects than glucose beverage and provide an equivalent carbohydrate challenge for diagnosis gestational diabetes.

2.2 Clinical Data to Date

There have been previous studies using glucose beverage alternatives including jelly beans and candy twists, with improved tolerance (fewer side effects of nausea, vomiting, bloating, diarrhea, sweating, headache) as reported by the patients. In a study using jelly beans for 50g 1-hr glucose challenge testing, side effects were reported in 38% of participants and 20% with jelly beans ($P < .001$), and were preferred by 76% of participants ($P < .001$).

However, previously used candy alternatives are limited by the varying portion size of conventional candy and have poor diagnostic accuracy.

Recently the makers of the standard glucose beverage used at our institution Jamp pharmaceuticals, issued a recall on a large number of their glucose beverage lots as they were not in compliance with the Health Canada standard that the actual glucose content of the drink is within 10% of the labeled glucose content (16). The supplier of glucose beverages for our institution has changed to Teva Pharmaceuticals as of June 1 2019. Dex4® regularly tests their lots and individual tablets to confirm consistency and accuracy of tablet size, hardness, and dextrose monohydrate content, and has agreed to provide a certificate of analysis for each lot of Dex4® tablets used in the trial (15).

2.3 Potential Risks/Benefits and Rationale

The participant population consists of 28 pregnant women between 24-32 weeks' gestation who have screened positive for gestational diabetes on the 50g glucose challenge test. The main drawback to participation is that women will have to undergo two fasting, 1 hour and 2 hour glucose values within one week. Risks involved with participating in the study include: possibility of pain, bruising, swelling or infection related to drawing blood, allergic reaction symptoms such as itching, facial swelling and anaphylaxis upon consumption if the participant has an allergy to corn based products such as dextrose. These risks will be minimized by screening patients for dextrose allergy before having them sign the informed consent form.

The benefit may not be directly to the patient as they will still need to complete the standard 75g glucose beverage test but they will be contributing to new knowledge on alternatives to the standard test that may benefit other pregnant women, including themselves, in the future.

The ultimate goal of this project is to improve women's health by 1) allowing more women to be screened for GDM and 2) providing an equivalent glucose beverage alternative with fewer side effects, making the screening process more comfortable for patients who cannot tolerate

glucose beverage. Improving the tolerability of the test is important because there is growing evidence that GDM significantly increases the risk of short and long term adverse consequences for both the fetus and the mother (10,11). Accurate diagnosis may allow women to implement preventative measures such as healthy lifestyle, which has shown to be effective in preventing T2DM in women with previous GDM (19,20). There have been recent quality control issues with the commercially available glucose beverage product (16), so this alternative test could become the standard test if the dose calibration is found to be more reliable.

3 STUDY OBJECTIVES

3.1 Primary Objective

Primary objective 1 (PO-1): to determine if Dex4® tablets is equivalent to glucose beverage for use in the 2-hr 75g OGTT in pregnant women between 24-32 weeks gestation who have screened positive for GDM.

3.2 Secondary Objective(s)

Secondary objective (SO-1): to determine if women have fewer side effects and prefer the standard (glucose beverage) OGTT test or the alternative (Dex4® tablets) OGTT test

4 STUDY DESIGN

4.1 General Design

Our project is a population-based, prospective randomized crossover study. Women who fall into the screen positive group of the 50g GCT (1 hour serum glucose of 7.8-11 mmol/L) will be offered participation in the study. 28 Participants will be recruited and will be randomly assigned using a pre-populated allocation table to take either the standard OGTT test (75g of glucose beverage) first or the alternative OGTT test (21 Dex4® tablets) first. The first test will be referred to as OGTT-1 and the second test will be referred to as OGTT-2. After completing OGTT-1 at the first test appointment, a questionnaire about pregnancy, health, diet and exercise habits, and side effects from the first test will be completed by the participant (Questionnaire A). After completing OGTT-2 at their second test appointment, a questionnaire about side effects from the second test and test preference will be completed by the participant (Questionnaire B). Each woman will complete both tests within one week and each subject will serve as their own control. Results will be kept blinded in the case report forms until both OGTT tests are done. Serum glucose will be measured using the same internationally standardised glucose-oxidase method (RocheDiagnosis) in the Sunnybrook Biochemistry lab. After serum glucose measurement, all results will be sent to the research team but only the standard of care glucose beverage test data will appear in electronic (or classical) medical records and be used for GDM diagnosis.

The following data will be collected by questionnaire at the first OGTT appointment:

- Estimated date of delivery
- # of previous pregnancies
- Previous diagnosis of GDM
- Pre-pregnancy weight (kg);
- Height (cm);
- Ethnic group (Caucasian, Indigenous, Hispanic, South Asian, East Asian, African, Middle Eastern, Other)
- History of macrosomic infant - ≥ 4000 g
- Polycystic ovary syndrome (yes-no);
- Medication (for corticosteroid use);
- First degree family history of T2DM
- Length of fast (hrs)
- Side effects (nausea, vomiting, headache, dizziness, sweating, other)

The following data will be collected by questionnaire at the second OGTT appointment:

- Side effects
- Preference for Dex4® or glucose beverage

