6.1.5 Participant Compliance Monitoring and Assessment

The participants will be observed taking the IP by the research staff and will not need to take the IP home or administer it on an ongoing basis. Participants who do not/are not able to take all 21 tablets or who vomit the tablets within 120 minutes will not be included in the primary outcome assessment. However, data regarding side effects will be retained for the secondary outcomes.

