10.2 Sample Size Considerations

Serum glucose values after a carbohydrate load have significant intra-individual variation, if done on the same person but at a different time the results can vary up to 16.7% (21) The two tests will be considered equivalent if the difference between them is less than or equal to 20%. For a mean one hour (+/- 15 minutes) post 75g carbohydrate load serum blood glucose of 10.6 mmol/L (standard deviation of 1.78 mmol/L) a sample of 28 will provide 80% power at alpha of 0.05 for a test of equivalence with Dex4® tablets assuming a 20% margin of equivalence. The sample size calculation was carried out using PASS Version 12 (Hintze, J. (2014). NCSS, LLC. Kaysville, Utah.) Accounting for loss to follow up of 33%, 42 women will need to be recruited, respectively. Based on data from Alberta, 20% of women screen positive on an 50g GCT (22). Approximately 230 women deliver at Sunnybrook every month, of those 45 will screen positive on the GCT. Assuming a 20% successful recruitment rate we should be able to complete recruitment in 4-6 months.

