10.4 Final Analysis Plan

Serum glucose values after a carbohydrate load have significant intra-individual variation, if done on the same person but at a different time the results can vary up to 16.7% (21) The two tests will be considered equivalent if the difference between them is less than or equal to 20%. For a mean one hour post 75g carbohydrate load serum blood glucose of 10.6 mmol/L (standard deviation of 1.78 mmol/L) a sample of 28 will provide 80% power at alpha of 0.05 for a test of equivalence with Dex4® tablets assuming a 20% margin of equivalence. The sample size calculation was carried out using PASS Version 12 (Hintze, J. (2014). NCSS, LLC. Kaysville, Utah.) Accounting for loss to follow up of 33%, 42 women will need to be recruited, respectively.

To evaluate equivalence, the mean of the differences at each time point (fasting, 1 hr and 2 hrs after glucose beverage/Dex4® tablets) will be calculated and a two-sample equivalence-test will be used to compare the means. Based on previous reports of intra-individual variation in 2 hour OGTT of 16.7% for blood glucose measurement (21), Dex4® tablets will be considered equivalent to glucose beverage if the equivalence margin is less than or equal to 20%.

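### Section 4.1 has 28 women recruited and randomised, while the sample size section needs 42 recruited to leave 28 evaluable

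*Protocol*

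**What the plan says.** Two places in the protocol give 28:

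- Section 4.1 (General Design): "28 Participants will be recruited and will be randomly assigned using a pre-populated allocation table".
- Section 2.3 (Potential Risks/Benefits and Rationale): "The participant population consists of 28 pregnant women".

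Four places separate the number needed from the number to recruit:

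- Protocol Summary, Sample Size row: "28 required by power calculation, aiming to recruit 42 (accounting for 33% loss".
- Section 10.2: "Accounting for loss to follow up of 33%, 42 women will need to be recruited". Section 5 (opening text) and section 10.4 say the same.

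Section 10.2 rests the 28 on a one-hour "serum blood glucose of 10.6 mmol/L (standard deviation of 1.78 mmol/L", and claims 80% power for 28 women, with alpha 0.05 and a 20% equivalence margin. Section 10.4 names the analysis: "a two-sample equivalence-test will be used to compare the means".

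Two further provisions show that the number entered and the number analysed will differ. Under section 5.3 a woman is enrolled when she signs consent, before either test. Section 6.1.5 drops from the primary analysis women who do not take all the tablets, and those "who vomit the tablets within 120 minutes will not be included in the primary outcome assessment".

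**The concern.** A protocol should give one enrolment number. Section 4.1 speaks of recruiting and randomising, which are counts at entry, so its 28 cannot be read as 28 completers. It conflicts directly with the 42 given elsewhere. Section 2.3 is weaker evidence because it does not mention recruitment, but a reader of the risk section, including an ethics board, would still take 28 as the number of women exposed.

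Two things are at stake. One is whether the study ends with the evaluable number on which its sample size statement rests. The other is whether the protocol is clear about how many women may be enrolled and how many assignments must be prepared. Section 4.1 mentions the number in the same sentence as the pre-populated allocation table, so someone preparing that table from 4.1 alone could stop at 28.

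**Working it through.** **Inputs**

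- Evaluable number required: 28 (Summary; sections 5, 10.2, 10.4).
- Loss: 33% (same places). Assumed here to cover every reason for not being evaluable. The text in sections 5, 10.2 and 10.4 calls it loss to follow-up, so exclusions under 6.1.5 might come on top.
- Recruited: 42 (same places) or 28 (section 4.1).
- Mean 10.6 and SD 1.78 mmol/L; margin 20%; alpha 0.05 (section 10.2).

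**1. The plan's recruitment figure reproduces.** Number to recruit = N/(1 - loss) = 28/0.67 = 41.8, rounded up to 42. In the other direction, 42 x 0.67 = 28.1. The inflation arithmetic is correct; the fault is that 4.1 and 2.3 do not carry it.

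**2. What 4.1 would deliver.** 28 x 0.67 = 18.8, about 19 evaluable women. Shortfall: 28 - 19 = 9.

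**3. Precision.** Interval width is proportional to 1/sqrt(n), so the ratio is sqrt(28/19) = 1.21, or about 21% wider. Including the t quantiles makes it about 1.24.

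**4. Power at 19.** Two one-sided t-tests, alpha 0.05 on each side, true difference zero, margin 0.20 x 10.6 = 2.12 mmol/L. Every woman takes both tests, so 19 women give 19 values per test.

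| Analysis of 19 women | Standard error (mmol/L) | df | Power |
|---|---|---|---|
| Two-sample, 19 values per test | 1.78 x sqrt(2/19) = 0.578 | 36 | 95% |
| Paired, within-woman correlation 0 | 1.78 x sqrt(2)/sqrt(19) = 0.578 | 18 | 94% |
| Paired, SD of the difference 1.78 (correlation 0.5) | 1.78/sqrt(19) = 0.408 | 18 | 99.9% |

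All three exceed the stated 80%. The protocol gives no SD for the within-woman difference, so the correlations are assumptions.

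**5. Which number fits the rest of the plan.** Sections 5 and 10.2 expect 45 screen-positive women a month and a 20% recruitment rate, so 45 x 0.20 = 9 a month. Then 42/9 = 4.7 months, inside the stated 4 to 6 months, while 28/9 = 3.1 months falls outside it. The accrual forecast was evidently made for 42.

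**The case against.** The strongest reply is that the intent is plain. Four places agree on 42, the Summary separates the two numbers explicitly, the accrual forecast fits 42, and nothing gives 4.1 precedence over the section devoted to sample size. On this view 4.1 simply carries the evaluable number into the wrong sentence. That is very likely how the error arose, and it is why the correction is easy. It does not make the sentence in 4.1 right, and a protocol should not leave its readers to choose between two enrolment totals.

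Two stronger readings are tempting and should be resisted.

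- *Power would fall to about 60%.* A reader might infer this from the calculation that comes closest to the stated 28: a parallel two-group equivalence test with 14 per group has 85% power (13 per group, 26 in total, already gives 81%), and 19 in total gives 60%. That splits 19 women into groups of about 9.5. It may explain where 28 came from, but it does not describe a crossover in which each woman contributes a value to both tests. Nor can 28 pairs plausibly be what gives 80%: that would need an SD of the difference of 3.74 mmol/L (power at 19 would then be 54%). With SD 1.78 on each test the SD of the difference cannot exceed 2 x 1.78 = 3.56, even at a correlation of -1.
- *Section 4.1 sets the length of the allocation table and the point at which recruitment stops.* The protocol does not say so. Sections 4.1 and 5.3.1 mention a pre-populated table without giving its length, and the stopping rules in 10.3 do not refer to 4.1. Stopping at 28 is a possible consequence of following 4.1, not a stated rule.

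**Conclusion.** The point stands as an internal contradiction: the number in 4.1 is wrong as written against the plan's own sample size, and 2.3 should be brought into line with it. If 4.1 were followed and the full 33% were lost, about 19 women would be evaluable instead of 28, with intervals about 21% wider.

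That size depends on recruitment actually stopping at 28 and on the loss reaching the planned 33%. The documents do not support a claim that power would drop below 80%. On the stated SD and margin, with no true difference and non-negative correlation between a woman's two results, it stays at about 94% or more. A true difference between the products, or a larger within-woman SD than the documents imply, would lower that figure. The case for correction rests on the contradiction and the loss of precision.

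**What to change.** In section 4.1, state that 42 women will be recruited and randomised in order to obtain 28 evaluable for the primary outcome. In section 2.3, give the same pair of numbers, so that the risk section shows how many women are to be enrolled. Confirm that the biostatistician's allocation table holds at least 42 entries. It would also help to say whether the 33% includes the exclusions in 6.1.5.

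The cost is wording, with ethics board review of the amendment as section 13.2 requires. No women are added beyond the 42 already stated, and no test procedure changes.

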8.5 Type and Duration of Follow-up for Adverse Events

AEs occurring as of the first administered dose of the investigational product and for a follow up period of 120 minutes after the last administered dose, will be collected. AEs recorded during

this period will be followed through to resolution, or until the event is assessed as chronic or stable.

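### The side-effect items do not name bloating, abdominal pain or diarrhea, three of the seven beverage side effects listed in the background, which risks incomplete capture in the secondary tolerability comparison

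*Protocol*

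**What the plan says.** Section 2.1 of the Protocol describes poor tolerance of the glucose beverage through seven symptoms: "nausea, vomiting, bloating, abdominal pain, diarrhea, sweating and headache". Section 2.2 describes the better tolerance of candy alternatives in earlier studies as "fewer side effects of nausea, vomiting, bloating, diarrhea, sweating, headache", so bloating and diarrhea appear there again.

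The data to be collected are narrower. Section 4.1 lists, for the first OGTT appointment, "Side effects (nausea, vomiting, headache, dizziness, sweating, other"; for the second appointment it says only that side effects are collected. Section 11.2 itemises the same five symptoms plus 'other' for both appointments. It treats these answers as source data, because no earlier record of them may exist.

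Side effects are a secondary outcome in section 4.3. The secondary objective in section 3.2 is "to determine if women have fewer side effects and prefer the standard (glucose beverage) OGTT test or the alternative" (the tablets), and section 10.1 hypothesises fewer side effects with the tablets.

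**The concern.** The Protocol says which symptoms make the beverage hard to tolerate, then sets a list for measuring tolerability that leaves out three of them. It adds dizziness, which neither section 2.1 nor section 2.2 mentions, and gives no reason for the difference.

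A symptom that is not an item on the form is recorded only if the woman volunteers it, or the person administering the form asks, and someone then classifies the entry. Such symptoms are likely to be recorded less completely than named ones. If so, a true difference between the tests in abdominal symptoms would look smaller than it is, in a trial whose planned evaluable sample is 28 women. The data are fixed at collection, and no later analysis can restore a symptom that was not recorded.

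**Working it through.** **1. The lists side by side**

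| Symptom | 2.1 (beverage) | 2.2 (earlier studies) | 4.1 and 11.2 (questionnaire items) |
|---|---|---|---|
| Nausea | yes | yes | yes |
| Vomiting | yes | yes | yes |
| Headache | yes | yes | yes |
| Sweating | yes | yes | yes |
| Bloating | yes | yes | no |
| Diarrhea | yes | yes | no |
| Abdominal pain | yes | no | no |
| Dizziness | no | no | yes |

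Of the seven symptoms in section 2.1, four are named on the questionnaire list and three are not: 3/7 = 43%. This is a share of symptom labels, not of symptom burden.

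**2. Whether adverse-event recording fills the gap**

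Section 8.3 allows specific questioning at each contact but gives no symptom list. It also lets the investigator leave unrecorded events that are common in this population irrespective of the product. Section 8.5 sets the collection window as "AEs occurring as of the first administered dose of the investigational product and for a follow up period of 120 minutes" after the last dose, and section 6.1 defines the investigational product as the tablets. The window is therefore not defined around the beverage test, and this route gives no balanced comparison.

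**3. What incomplete write-in would do**

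The Protocol gives no figure for this, so there is none to reproduce. The inputs are:
- Rates of 38% and 20%, from section 2.2 (a 50 g, 1-hour jelly-bean study). The sentence there does not label the 38%; I read it as the beverage. Difference: 38 − 20 = 18 points.
- f = 0.30, the share of symptomatic women whose only symptoms are the three unlisted ones. Assumption, taken as equal for both tests.
- r, the share of those women whose symptoms are written in under 'other'. Assumption, varied from 1 to 0 and taken as equal for both tests.

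Observed rate = true rate × [1 − f(1 − r)]. The observed difference shrinks by the same factor.

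| r | Factor | Beverage | Alternative | Difference |
|---|---|---|---|---|
| 1.00 | 1.000 | 38.0% | 20.0% | 18.0 points |
| 0.75 | 0.925 | 35.2% | 18.5% | 16.7 points |
| 0.50 | 0.850 | 32.3% | 17.0% | 15.3 points |
| 0.00 | 0.700 | 26.6% | 14.0% | 12.6 points |

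The ratio of the two rates does not change: 20/38 = 0.53 and 14.0/26.6 = 0.53. For the three symptoms taken alone, the observed rates and their difference are r times the true values.

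**4. Scale against sampling error**

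With n = 28 and the same two rates, the variance of a paired difference is [0.38 × 0.62 + 0.20 × 0.80 − 2ρ√(0.2356 × 0.16)]/28, where ρ is the within-woman correlation (assumed).
- ρ = 0: 0.3956/28 = 0.01413, SE 0.119, 95% half-width 1.96 × 0.119 = 23 points.
- ρ = 0.5: (0.3956 − 0.1942)/28 = 0.00719, SE 0.085, half-width 17 points.

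The largest illustrated loss, 18.0 − 12.6 = 5.4 points, is well inside either half-width.

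**The case against.** The strongest reply is that nothing is lost for certain. The list ends in 'other', so all three symptoms can be recorded, and with complete write-in there is no loss. The questionnaire forms are not shown. Section 4.1 says the participant completes them and section 7.2 says staff administer them, so staff might probe the open item. All of this stands, and it limits the point to a risk. It does not explain why symptoms the Protocol itself treats as typical are not items.

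A reader might infer that the tolerability result will be biased towards one product. The documents do not support that. Section 11.2 gives the same list at both appointments and each woman is her own control, so a shortfall common to both tests shrinks a difference without creating one. If anything it works against the hypothesis of fewer side effects. One reservation remains: the study is open-label (section 5.3.2), so write-in could differ by test, but nothing shows that it would.

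A reader might also infer that the three symptoms are where the Protocol most expects a benefit, because section 2.1 cites "variety of flavours and lack of carbonation". That section also cites the solid, chewable form and does not link any of these features to bloating or another particular symptom. The link to bloating is plausible but is the reader's own.

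It is also fair that side effects are secondary, that the sample size rests on glucose, that preference is a second measure of acceptability, and that the illustrated loss is small beside sampling error. Nor would a named item capture symptoms that begin after the appointment at which the form is completed. These facts limit the importance of the point. They are not reasons to keep the shorter list, since the change costs almost nothing and the data cannot be recovered later.

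**Conclusion.** The point holds as a risk to the completeness of a secondary outcome. The omission is exact: three of the seven beverage side effects in section 2.1 are left to 'other' in sections 4.1 and 11.2. The expected consequence is reduced sensitivity in the side-effect comparison. The primary glucose comparison is not affected.

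The Protocol does not allow the loss to be sized. The range of 18.0 to 12.6 points depends on rates borrowed from a different test, an assumed 30% of symptomatic women having only the unlisted symptoms, and equal write-in for both tests. It shows direction and rough scale only. That the symptoms will in fact be under-counted is not established.

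**What to change.** Add bloating, abdominal pain and diarrhea as named side-effect items on Questionnaire A and Questionnaire B, and keep 'other'. In section 4.1, itemise the list for the second appointment as well as the first. Make the same change under both appointments in section 11.2, so that the list stays identical for the two tests and agrees with section 2.1.

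The cost is three more items on each of two paper forms, with no extra visit, blood sample or participant.
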